8.1.1.3 Primary Safety Endpoint(s)

This study does not have primary safety endpoints.

(Amended 4 April 2018)

8.1.2 Secondary Endpoint(s)

8.1.2.1 Secondary Effectiveness Endpoint(s)

This study does not have secondary effectiveness endpoints.

(Amended 4 April 2018)

_

¹ Serogroup B test strains to be used in the study: M14459 (fHbp), 96217 (NadA), NZ98/254 (PorA) and M07-0241084 (NHBA)

8.1.2.2 Secondary Immunogenicity Endpoint(s)

The following will be summarized at Days 1 (except four-fold rise), 6 and 31 for follow-on subjects, and at Days 1, 31, 66 and 91 for naive subjects

- Percentages of subjects with HT-hSBA titers ≥ LLOQ and differences between groups against each of four serogroup B test strains¹ and serogroups A, C, W and Y (only after MenABCWY vaccination).
- HT-hSBA GMTs and group ratios against each of four serogroup B test strains¹ and serogroups A, C, W and Y (only after MenABCWY vaccination), and GMRs (Day 6/Day1 and Day 31/Day 1 for follow-on subjects; Day 31/Day 1, Day 66/Day 1 and Day 91/Day 1 for naive subjects).
- Percentages of subjects with four-fold rise² in HT-hSBA titers and group differences, against each of four serogroup B test strains¹ and serogroups A, C, W and Y (only after MenABCWY vaccination).

(Amended 4 April 2018)

8.1.2.3 Secondary Safety Endpoint(s)

Safety of the study vaccines will be assessed in all subjects in terms of the percentages of subjects with reported adverse events including:

- Any solicited and unsolicited AEs reported within 30 minutes after vaccination at Day 1 (for all subjects) and also Day 61 (for naive subjects only);
- Solicited local and systemic AEs reported from Day 1 (6 hours) to Day 7 after vaccination at Day 1 (for all subjects) and Day 61 *to Day* 67 (for naive subjects);
- Other indicators of reactogenicity (e.g. use of analgesics / antipyretics, body temperature) within 7 days after vaccination at Day 1 (for all subjects) and Day 61 (for naive subjects);
- Unsolicited AEs reported from Day 1 to Day 31 for all subjects and Day 61 to Day 91 for naive subjects;

_

¹ Serogroup B test strains to be used in the study: M14459 (fHbp), 96217 (NadA), NZ98/254 (PorA) and M07-0241084 (NHBA).

² For subjects with prevaccination hSBA titers \leq LLOQ, a post-vaccination hSBA \geq 4 times the LLOQ; for subjects with prevaccination hSBA titers \geq LLOQ, an increase of at least 4 times the prevaccination hSBA.

- Medically-attended AEs reported during the entire study period (up to **D**ay 181 for follow-on subjects and up to Day 241 for naive subjects);
- AEs leading to premature withdrawal from the study during the entire study period (up to **D**ay 181 for follow-on subjects and up to Day 241 for naive subjects);
- SAEs reported during the entire study period (up to **D**ay 181 for follow-on subjects and up to Day 241 for naive subjects).

(Amended 4 April 2018)

8.1.3 Exploratory Endpoint(s)

8.1.3.1 Exploratory Effectiveness Endpoint(s)

This study does not have exploratory effectiveness endpoints.

(Amended 4 April 2018)

8.1.3.2 Exploratory Immunogenicity Endpoint(s)

This study does not have exploratory immunogenicity endpoints.

8.1.3.3 Exploratory Safety Endpoint(s)

This study does not have exploratory safety endpoints.

8.2 Success Criteria

8.2.1 Success Criteria for Primary Objective(s)

8.2.1.1 Success Criteria for Primary Effectiveness Objective(s)

Not applicable

(Amended 4 April 2018)

8.2.1.2 Success Criteria for Primary Immunogenicity Objective(s)

This study does not have success criteria for the primary objectives.

(Amended 4 April 2018)

8.2.1.3 Success Criteria for Primary Safety Objective(s)

Not applicable.

8.2.2 Success Criteria for Secondary Objective(s)

This study does not have success criteria for secondary objectives.

8.2.2.1 Success Criteria for Secondary Effectiveness Objective(s)

Not applicable.

(Amended 4 April 2018)

8.2.2.2 Success Criteria for Secondary Immunogenicity Objective(s)

This study does not have success criteria for secondary immunogenicity objectives.

8.2.2.3 Success Criteria for Secondary Safety Objective(s)

This study does not have success criteria for secondary safety objectives.

8.3 Analysis Sets

8.3.1 All Enrolled Set

All screened subjects who provide informed consent and provide demographic and/or baseline screening assessments, regardless of the subject's randomization and treatment status in the study and received a Subject ID.

8.3.2 Exposed Set

All subjects in the enrolled set who receive a study vaccination.

8.3.3 Safety Set

Solicited Safety Set (solicited local and systemic adverse events and other solicited adverse events)

All subjects in the Exposed Set with any solicited adverse event data and/or indicators of solicited adverse events.

Unsolicited Safety Set (unsolicited adverse events)

All subjects in the Exposed Set with unsolicited adverse event data.

Overall Safety Set

All subjects who are in the Solicited Safety Set and/or Unsolicited Safety Set.

Subjects will be analyzed as "treated" (i.e., according to the vaccine a subject received, rather than the vaccine to which the subject may have been randomized).

8.3.4 Full Analysis Set (FAS) Immunogenicity Set

Full Analysis Set Immunogenicity

Full Analysis Set Persistence (24 months after last vaccination in V102 15) – FAS Persistence (Day 1)

All subjects in the All Enrolled Set, who are randomized (if naive), and:

• Provide evaluable serum sample with results for at least one serogroup B test strain or serogroups A, C, W or Y at Day 1 in the extension study.

Full Analysis Set Immunogenicity (Day 31, after booster dose [follow-on]/first dose [naive]) – FAS Immunogenicity (Day 31)

All subjects in the All Enrolled Set, who are randomized (if naive), and:

- Receive at least one study vaccination and,
- Provide evaluable serum sample with results for at least one serogroup B test strain or serogroups A, C, W or Y (only after MenABCWY vaccination) at Day 31 in the extension study.

Full Analysis Set Immunogenicity (Days 6 and 31, after booster dose [follow-on]/ Days 66 and 91 after second dose [naive]) – FAS Immunogenicity (Days 6, 31/Days 66, 91)

All subjects in the All Enrolled Set, who are randomized (if naive), and:

- Receive at least one study vaccination and,
- Provide evaluable serum sample with results for at least one serogroup B test strain or serogroups A, C, W or Y (only after MenABCWY vaccination) at Day 1, and in addition at least at Day 6 or Day 31 (follow-on subjects) / Day 66 or Day 91 (naive subjects) in the extension study.

In case of vaccination error, subjects in the FAS sets will be analyzed "as randomized" (i.e., according to the vaccine a subject was designated to receive, which may be different from the vaccine the subject actually received).

(Amended 4 April 2018)

8.3.5 Per Protocol (PP) Set Immunogenicity Set

Per Protocol (PP) Set Immunogenicity

All subjects in the FAS Immunogenicity who:

- Correctly receive all meningococcal vaccinations in the parent study (persistence objective) /all meningococcal vaccinations in the parent study and vaccinations relevant for the objective¹ in the extension study (rest of immunogenicity objectives) and,
- Have no protocol deviations leading to exclusion (see section 8.3.8, Protocol Deviations) as defined prior to analysis and,
- Are not excluded due to other reasons defined prior to analysis (see section 8.3.8, Protocol Deviations).

Additional requirements:

Per Protocol Set Immunogenicity (Days 6 and 31, after booster dose [follow-on]/ Days 66 and 91 after second dose [naive]) – PPS Immunogenicity (Days 6, 31/Days 66, 91)

All subjects in the PPS *Immunogenicity* who:

• Provide evaluable serum sample with results for at least one serogroup B test strain or serogroups A, C, W or Y (only after MenABCWY vaccination) at Day 1, Day 6 and Day 31 (follow-on subjects) / Day 1, Day 66 and Day 91 (naive subjects) in the extension study.

PPS are subsets of FAS and should be always defined even if the objectives do not require it.

¹ Booster dose (follow-on) and first dose (naive in secondary objectives *1* and *3*) / first and second dose (naive in secondary objectives *2* and *4*). Further details will be provided in the Statistical Analysis Plan.

Subjects might be excluded due to other reasons than protocol deviations (e.g., subjects who withdrew informed consent).

(Amended 4 April 2018)

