8.4.3.2.2 Analysis Sets

The analysis set to be used for all secondary immunogenicity objectives is the Full Analysis Set. Analysis of the objectives will, in any case, be based on both the Full Analysis Set and the Per Protocol Set.

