# All subjects in the PPS Persistence who:

• Provide evaluable serum sample with results for at least one serogroup B test strain or serogroups A, C, W or Y (only after MenABCWY vaccination) at each visit on Day 1, Day 6 and Day 31 (follow-on subjects) / Day 1, Day 66 and Day 91 (naive subjects) in the extension study.

PPS are subsets of FAS and should be always defined even if the objectives do not require it.

\_

<sup>5 Booster dose (follow-on) and first dose (naive in secondary objectives 2 and 4) / first and second dose (naive in secondary objectives 3 and 5).

Subjects might be excluded due to other reasons than protocol deviations (e.g., subjects who withdrew informed consent).

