# 7.7 Overview of Analysis Sets by PD Code

Table 7.7-1: Safety Sets

PD code	PD Description	Study Objective/ Period	All Exposed Set	Overall Safety Set	Safety Set, Solicited AEs, Period 1, T6H-D7	Safety Set, Solicited AEs, Period 2, T6H-D7	Unsolicited Safety set
	Exclusion code		EXPFL	SAFFL	SSS10FL	SSS11FL	SSU10FL
100	Study vaccine not administered AT ALL	All Study	EXC	EXC	EXC	EXC	EXC
115	Subject did not provide any post-vaccination unsolicited safety data	All Study					EXC
116.1	Subject did not provide any post-vaccination solicited safety data after vaccination 1	All Study (follow on)/First vaccination (Naive)			EXC		
116.2	Subject did not provide any post-vaccination solicited safety data after vaccination 2*	Second vaccination				EXC	

EXC = excluded from this analysis set.

\*applicable to naive subjects only.

PD code	PD Description	Study objective/ period	FAS IMM Persistence (Day 1)	FAS IMM (Day 31)	FAS IMM (Days 6, 31/Days 66, 91)	PPS IMM Persistence (Day 1)	PPS IMM (Day 31)	PPS IMM (Days 6, 31/Days 66, 91)
	Exclusion code		FAS10FL	FAS11FL	FAS12FL	PPS10FL	PPS11FL	PPS12FL
100	Study vaccine not administered AT ALL	Day 1 – End of study		EXC	EXC		EXC	EXC
110. 100	Serological results (A, C, W, Y and 4 B strains) are not available  Visit not done, blood draw not done	Day 1	EXC		EXC	EXC		EXC
110.d.102	Serology results are not available  Serological results (A, C, W, Y and 4 B strains) are not available	Day 1	EXC		EXC	EXC		EXC
110. 200	Serological results (A, C, W, Y and 4 B strains) are not available  Visit not done, blood draw not done	Day 6 (follow on) Day 66 (naive)			EXC			EXC
110.d.202	Serology results are not available  Serological results (A, C, W, Y and 4 B strains) are not available	Day 6 (follow on) Day 66 (naive)			EXC			EXC

	lential	

PD code	PD Description	Study objective/ period	FAS IMM Persistence (Day 1)	FAS IMM (Day 31)	FAS IMM (Days 6, 31/Days 66, 91)	PPS IMM Persistence (Day 1)	PPS IMM (Day 31)	PPS IMM (Days 6, 31/Days 66, 91)
110. 300	Serological results (A, C, W, Y and 4 B strains) are not available  Visit not done, blood draw not done	Day 31		EXC	EXC (follow on only)		EXC	EXC (follow on only)
110.d.302	Serology results are not available  Serological results (A, C, W, Y and 4 B strains) are not available	Day 31		EXC	EXC (follow on only)		EXC	EXC (follow on only)
110. 500	Serological results (A, C, W, Y and 4 B strains) are not available  Visit not done, blood draw not done	Day 91			EXC (naive only)			EXC (naive only)

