110.d.502	Serology results are not available Serological results (A, C, W, Y and 4 B strains) are not available	Day 91			EXC (naive only)			EXC (naive only)
112.102	Obvious deviation from Laboratory Manual or error in laboratory data (HT-SBA)	Day 1				EXC		EXC
112.202	Obvious deviation from Laboratory Manual or error in laboratory data (HT-SBA)	Day 6 (follow on) Day 66 (naive)						EXC

PD code	PD Description	Study objective/ period	FAS IMM Persistence (Day 1)	FAS IMM (Day 31)	FAS IMM (Days 6, 31/Days 66,	PPS IMM Persistence (Day 1)	PPS IMM (Day 31)	PPS IMM (Days 6, 31/Days 66,
112.302	Obvious deviation from Laboratory Manual or error in laboratory data (HT-SBA)	Day 31			91)		EXC	EXC (follow on only)
112.502	Obvious deviation from Laboratory Manual or error in laboratory data (HT-SBA)	Day 91						EXC (naive only)
120.100	Randomization failure to treatment	Day 1				EXC (naive only)	EXC (naive only)	EXC (naive only)
140.100	Vaccination not according to protocol	Day 1				EXC	EXC	EXC
140.300	Vaccination not according to protocol	Day 61 (Naive only)						EXC (naive only)
150.100	Administration of forbidden vaccine	Day 1 (before BS_1)				EXC	EXC	EXC
150.300	Administration of forbidden vaccine	Day 1 (after BS_1)- day 7					EXC	EXC
150.500	Administration of forbidden vaccine	-7/+7 2 nd vaccination (naive only)						EXC (naive only)
200	Subject did not meet entry criteria	Day 1 – end of study				EXC	EXC	EXC

PD code	PD Description	Study objective/ period	FAS IMM Persistence (Day 1)	FAS IMM (Day 31)	FAS IMM (Days 6, 31/Days 66, 91)	PPS IMM Persistence (Day 1)	PPS IMM (Day 31)	PPS IMM (Days 6, 31/Days 66, 91)
220	Subject had contraindication for a subsequent study vaccination but was vaccinated	Day 1- Day 61 (naive only)						EXC
230.101	Administration of forbidden medication	Day 1				EXC	EXC	EXC
230.102	Administration of forbidden medication: ANTIBIOTICS	Day 1 (before BS_1)				EXC		
230.201	Administration of forbidden medication	Day 6 (follow on) Day 66 (naive)					EXC (follow on only)	EXC
230.202	Administration of forbidden medication: ANTIBIOTICS	Day 6 (follow on) Day 66 (naive)						EXC
230.301	Administration of forbidden medication	Day 31					EXC	EXC
230.302	Administration of forbidden medication: ANTIBIOTICS	Day 31 (before BS_2)					EXC	EXC (follow on only)
230.501	Administration of forbidden medication	Day 91						EXC (naive only)
230.502	Administration of forbidden medication: ANTIBIOTICS	Day 91						EXC (naive only)

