240	Underlying medical condition forbidden by the protocol	Day 1- end of study				EXC	EXC	EXC

$\sim$	~		
Con	†10	en:	tıa.
COL		$\iota\iota\iota\iota\iota$	ши.

PD code	PD Description	Study objective/ period	FAS IMM Persistence (Day 1)	FAS IMM (Day 31)	FAS IMM (Days 6, 31/Days 66, 91)	PPS IMM Persistence (Day 1)	PPS IMM (Day 31)	PPS IMM (Days 6, 31/Days 66, 91)
260.100	Did not comply with study vaccination schedule	Day 1					EXC	EXC
260.200	Did not comply with study vaccination schedule	Day 61 (naive only)						EXC
270.100	Did not comply with blood draw schedule*	Day 1				EXC		EXC
270.200	Did not comply with blood draw schedule	Day 6 (follow on) Day 66 (naive)						EXC
270.300	Did not comply with blood draw schedule*	Day 31					EXC	EXC (follow on only)
270.400	Did not comply with blood draw schedule	Day 91						EXC (naive only)

\*e.g. BD after vaccination

FAS = Full Analysis Set; PPS=Per Protocol Set; EXC = excluded from this analysis set.

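### The supporting post-dose per-protocol set requires samples at all three visits, so a fault at one post-dose visit drops a valid titre at the other; the SAP 7.7 table also contradicts the FAS definition on missing samples

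*Protocol*

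**What the plan says.** Protocol 8.3.5 adds a condition to the combined post-dose per-protocol set (Days 6, 31/Days 66, 91): a result "at Day 1, Day 6 and Day 31 (follow-on subjects) / Day 1, Day 66 and Day 91 (naive subjects". SAP 7.4 has the same rule and makes the conjunction explicit: "at each visit on Day 1, Day 6 and Day 31 (follow-on subjects) / Day 1, Day 66 and Day 91 (naive subjects". SAP 7.4 also nests this set inside PPS Persistence, which itself depends on a Day 1 result.

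The immunogenicity table in SAP 7.7 puts the rule into deviation codes. A Day 6/66 problem excludes the subject from the whole combined PPS under any of these:
- 110.200 ("Visit not done, blood draw not done") and 110.d.202 (no serology result);
- 112.202 ("Obvious deviation from Laboratory Manual or error in laboratory data (HT-SBA");
- 230.202 ("Administration of forbidden medication: ANTIBIOTICS");
- 270.200 ("Did not comply with blood draw schedule").

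The corresponding Day 31 codes (follow-on only) and Day 91 codes (naive only) exclude from the same set.

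The combined FAS in protocol 8.3.4 and SAP 7.3 is looser. It asks for a Day 1 result "and in addition at least at Day 6 or Day 31 (follow-on subjects) / Day 66 or Day 91 (naive subjects". Protocol 8.4.3.2.2 makes the FAS the set for the secondary immunogenicity objectives and adds: "Analysis of the objectives will, in any case, be based on both the Full Analysis Set and the Per Protocol Set".

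Day 31 has its own FAS and PPS flags (FAS11FL, PPS11FL). Days 6, 66 and 91 appear only in the combined flags (FAS12FL, PPS12FL). Protocol 8.3.6 and SAP 7.6 define no other sets.

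**The concern.** The endpoints in protocol 8.1.2.2 are reported visit by visit. The percentage at or above LLOQ and the GMT at a visit need only that visit's sample; the GMR and the four-fold rise add Day 1. None of them at Day 91 uses Day 66, yet a Day 66 fault removes the subject from the only per-protocol estimate at Day 91.

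Two things are at stake. First, usable data leave a reported analysis. Second, the Day 91 per-protocol group is selected on what happened at another visit. Day 66 has a draw window of -1 to +3 days, against -7 to +10 for Day 91 (protocol Table 6). Protocol 4.3 delays a draw when systemic antibiotics were taken less than 3 days before, so a course running at Day 66 could push the draw outside its window or, if the draw goes ahead, trigger the antibiotic code. SAP 8.2.2 assumes missing immunogenicity values are MCAR and plans no imputation.

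The FAS contradiction matters separately because it concerns the lead set.

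**Working it through.** **Comparing the definitions, for a naive subject with valid Day 1 and Day 91 results and a problem only at Day 66**

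| Problem at Day 66 | Combined FAS, by definition | Combined FAS, by SAP 7.7 table | Combined PPS, definition and/or table |
|---|---|---|---|
| No sample or result (110.200, 110.d.202) | kept | excluded | excluded |
| Laboratory fault (112.202) | kept | kept | excluded |
| Antibiotics (230.202) | kept | kept | excluded |
| Off schedule (270.200) | kept | kept | excluded |

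The first row is the contradiction. It recurs in mirror image: 110.300 and 110.d.302 (follow-on) and 110.500 and 110.d.502 (naive) exclude from the combined FAS a subject who still has Day 1 and Day 6/66 results. SAP 6.2 says the deviation listings are programmed from this table's codes, so the table could prevail in practice.

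The table already separates visits elsewhere. Sample codes for Day 31 reach the combined PPS for follow-on subjects only, so a naive Day 31 fault does not touch Day 91. The four kinds of Day 6/66 sample code above do not touch PPS (Day 31). Only the pairs Day 6 with 31 and Day 66 with 91 are tied together.

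**Size**

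The current plan states no evaluable number or power (protocol 8.5), so there is no figure to reproduce.

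Inputs: n = 100 per naive arm (200 randomized 1:1); d = proportion of samples lost per visit, **assumed** 2%, 5% or 10% and independent between visits, because the current text gives no rate.

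- All three visits: 100(1-d)³
- Day 1 plus Day 91: 100(1-d)²
- Day 91 alone: 100(1-d)
- CI width scales roughly with 1/√n. Widening against Day 1 plus the visit is √[1/(1-d)]; against the visit alone it is 1/(1-d).

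| d | All three | Day 1 + Day 91 | Day 91 alone | Wider than Day 1 + visit | Wider than visit alone |
|---|---|---|---|---|---|
| 2% | 94.1 | 96.0 | 98.0 | 1.01 | 1.02 |
| 5% | 85.7 | 90.2 | 95.0 | 1.03 | 1.05 |
| 10% | 72.9 | 81.0 | 90.0 | 1.05 | 1.11 |

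Subjects with a valid Day 91 titre dropped by the all-visits rule, per 100: 98.0 - 94.1 = 3.9; 95.0 - 85.7 = 9.3; 90.0 - 72.9 = 17.1. The part due to Day 66 alone is 1.9, 4.5 and 8.1, about half; the rest is due to Day 1.

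Clopper-Pearson half-width at an assumed 70% rate:
- d = 5%: 10.1 points (n = 86), 9.9 (n = 90), 9.7 (n = 95).
- d = 10%: 11.0 points (n = 73), 10.4 (n = 81), 9.9 (n = 90).

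If Day 66 loses 10% and the other two visits 5%: 100 × 0.95 × 0.90 × 0.95 = 81.2 remain. Against Day 1 plus Day 91 (90.25) the widening is √(90.25/81.2) = 1.05; against Day 91 alone (95) it is √(95/81.2) = 1.08.

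**The case against.** The best defence is that this is a supporting set in a descriptive, secondary analysis. The FAS leads; the study has no hypotheses or success criteria for these objectives; no conclusion rule depends on the per-protocol numbers. Objectives 2 and 4 describe a series of visits, and a completers' set keeps the same subjects at every time point, which is a legitimate choice beside a looser FAS. All of that stands. It limits the weight of the point, but it gives no reason to make this the only per-protocol set for naive Day 91, since a common cohort can be kept alongside.

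The independence assumption also overstates the loss. A subject who leaves before Day 66 has no Day 91 titre to lose, so positively correlated losses shrink the effect.

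A reader might infer more than the documents support:
- *That a Day 66 fault deletes the Day 91 titre from the trial.* It does not. The FAS definition retains it, and codes 112.202, 230.202 and 270.200 exclude from the PPS only. Only the missing-sample codes reach the FAS, and there the table conflicts with the text.
- *That Day 91 is the key visit.* Objectives 2 and 4 list Day 66 and Day 91 together and rank neither.
- *That naive subjects are treated worse by design.* Within objectives 2 and 4 both populations face the same three-visit rule. The Day 31 set serves objectives 1 and 3 and covers naive Day 31 too; that it also protects follow-on Day 31 is a by-product.

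**Conclusion.** The point holds for the combined post-dose PPS: a fault at one post-dose visit removes a valid titre at the other, and naive Day 91 has no other per-protocol set. SAP 6.1 allows part of a subject's data to be excluded, but the SAP 7.7 table assigns one flag across both visits and gives no visit-level rule.

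The precision cost is modest: CIs about 1%, 3% or 5% wider than with Day 1 plus the visit, or 2%, 5% or 11% wider than with the visit alone, at assumed independent losses of 2%, 5% or 10%, and less under correlated loss. Under the plan's own MCAR assumption that is the whole cost; any selection effect requires a departure from MCAR, and the documents give no basis for sizing it. That 270.200 follows the visit window in protocol Table 6 is also an assumption, since the SAP does not define the limit.

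Separately, the table and the FAS definition disagree on a single missing post-dose sample. This must be reconciled whatever is decided about the PPS, because it changes who is in the lead set.

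**What to change.** 1. Define the post-dose PPS by visit: Day 6, Day 31, Day 66 and Day 91.
2. Apply each sample-level code (110, 112, 270 and the antibiotic 230 codes) only to its own visit. The 230 codes for other forbidden medication do not describe a sample fault, and this point does not call for changing them.
3. Choose how to treat Day 1. Either require it only for the GMR and four-fold rise, which means defining matching visit-level FAS sets and no longer nesting the post-dose PPS in PPS Persistence; or keep Day 1 throughout, so that the PPS stays a subset of the existing FAS. The second is simpler and still removes the dependence between post-dose visits. The first has a precedent: the table does not exclude a subject without a Day 1 result from PPS (Day 31).
4. Correct the SAP 7.7 table so that 110.200, 110.d.202 and the matching Day 31 and Day 91 codes do not by themselves exclude a subject from the combined FAS. Exclusion should follow only when both post-dose results, or Day 1, are missing.
5. Keep the all-visits set as supportive for the time course.

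The cost is an edit to protocol 8.3.5, SAP 7.4 and the SAP 7.7 table, plus three more PPS flags (and FAS flags if Day 1 is dropped). N will differ slightly between visits in the per-protocol tables. No data collection changes.
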